During the first presentation at the outpatient clinic the surgeon (with sufficient experience in treatment of UCL injuries) confirms the diagnosis complete UCL rupture by physical examination. Laxity of the MCP joint is examined by providing radial force to the proximal phalanx, while stabilizing the thumb metacarpal bone. Stressing the MCP joint in the acute setting may be painful and quarding or muscle spasm may give a false-negative examination. Local anesthesia can be injected into the MCP joint to allow for better examination, when indicated. When the diagnosis of a complete UCL rupture is confirmed (according to the criteria provided under the inclusion criteria), the patient meets the inclusion criteria and has provided informed consent, the patient is randomized. Baseline outcome measures are evaluated in the form of surveys. If feasible at the study site, an ultrasound of the thumb is planned prior to application of a new cast to confirm the diagnosis for study purposes. The outcome of the ultrasound is blinded for the patients as well as for the surgeon. A new cast to immobilize the MCP, in 10-30 degrees (slight) flexion (neutral position), and the CMC joint, in 30-40 degrees palmar abduction, is applied (IP joint is free). Patients will be immobilized for a total period of 4 weeks, including the period between ED and outpatient clinic. After 4 weeks the immobilization cast will be replaced by a removable cast for a period of 4 weeks. Two weeks after the start of immobilization, a second appointment is scheduled to repeat examination of the thumb.

3) Repeat examination at the hand surgery outpatient clinic 2 weeks after ED visit. Laxity of the MCP joint is re-examined by a hand surgeon. The hand surgeon examines if 'tightening' of the UCL has occurred by applying radial deviation stress to the dumb. The chance that re-examination at 2 weeks will induce a re-rupture or a Stener Lesion is close to zero, as re-examination at this time is also part of the current clinical practice in case of

V7 01-02-2024 14 of 30

cast immobilization. 'Tightening' is not a subtle finding and might even be present with less opening during radial deviation stress when compared to the contralateral thumb.

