- When the hand surgeon concludes that there is a firm endpoint (meaning adequate healing of the UCL ligament) cast immobilization is continued for another 2 weeks, until a total immobilization period of 4 weeks is completed. An appointment is scheduled after 4 weeks of cast immobilization.
- When there is no firm endpoint of the UCL or there is doubt about a firm endpoint, patients are scheduled for surgery within 5 working days (switching to usual care; see description usual care).

4) Outpatient clinic visit after 4 weeks of immobilization

The patient visits the hand surgeon. The immobilization cast is removed and replaced for a removable cast, which allows the patient to start exercising. Patients are instructed to start using the thumb for regular daily activities, without putting pressure on it, and start thumb exercises consisting of a combination of opposition and abduction/adduction movements. Patients are advised to repeat the exercises 5-10 times a day. A referral is made to the hand therapist to guide this process. Hand therapy will start within 1 week. The frequency and duration of hand therapy will be determined by the hand therapist. Hand therapists from all hospitals will collaborate to achieve consensus on a treatment protocol. Outcome measures are evaluated in the form of physical examination and surveys. A new appointment is scheduled at 3 months.

- 5) Visit to outpatient clinic at 3 months (standard visit)
 Progression of treatment is evaluated with the patient and expectations are managed.
 Outcome measures are evaluated in the form of physical examination and surveys. A new appointment is scheduled at 6 months.
- 6) Visit to outpatient clinic at 6 months (standard visit)
 Progression of treatment is evaluated with the patient and expectations are managed
 Outcome measures are evaluated in the form of physical examination and surveys. A
 new appointment is scheduled at 12 months.
- 7) Visit to outpatient clinic at 12 months (visit for study purpose)

 Treatment outcome is evaluated for study purposes. Outcome measures are evaluated in the form of physical examination and surveys.

USUAL CARE/COMPARISON

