The Dutch hand fracture guideline committee recommends operative treatment for patients with a complete UCL rupture, including Stener Lesions, and postoperative management with cast immobilization. [6] Patients will receive surgical treatment of the thumb. Postoperative management consists of cast immobilization of the MCP and CMC joint in neutral position for 4 weeks, followed by a removable cast for 4 weeks. The treatment details, from first presentation to full recovery are described step-by-step.

1) First presentation at the ER (pre-treatment protocol) This pre-treatment protocol applies to patients who present at the ED with a sustained trauma to the thumb, resulting in acute pain and swelling around the MCP joint of the thumb. These patients are potentially eligible for inclusion in the study and receive a temporary cast that immobilizes the MCP and CMC joint of the thumb.

V7 01-02-2024 15 of 30

Patients will be instructed not to use the thumb during this period. An appointment with the surgeon is scheduled within 3-5 days from presentation at the ED.

2) First presentation at the outpatient clinic (start treatment usual care)

During the first presentation at the outpatient clinic the surgeon confirms the diagnosis complete UCL rupture by physical examination. Laxity of the MCP joint is examined by providing radial force to the proximal phalanx, while stabilizing the thumb metacarpal bone. Stressing the MCP joint in the acute setting may be painful and guarding or muscle spasm may give a false-negative examination. Local anesthesia can be injected into the MCP joint to allow for getter examination when indicated. When the diagnosis of a complete UCL rupture is confirmed (according to the criteria provided under the inclusion criteria), the patient meets the inclusion criteria and has provided informed consent, the patient is randomized. Baseline outcome measures are evaluated in the form of surveys. Surgery is scheduled within 5 working days after the outpatient clinic visit. In the meantime, a new cast to immobilize the MCP and CMC joint is applied. If feasible at the study site, an ultrasound of the thumb is planned prior to surgery to confirm the diagnosis for study purposes. The outcome of the ultrasound is blinded for the patients as well as for the surgeon.

3) Surgery

In general, two surgical techniques are described in literature and used in daily clinical practice:

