7. STATISTICAL ANALYSIS

Data will be analyzed following intention-to-treat. Categorical variables will be presented as counts and percentages and continuous variables as median and interquartile ranges or mean and standard deviation based on the normality of the data. Differences in characteristics between groups will be compared using Fisher exact and Pearson's χ^2 tests for categorical variables, and Wilcoxon rank sum tests and unpaired t test will be used for continuous variables, where appropriate.

We will conduct a linear regression analysis for longitudinal data (i.e. a mixed model) in which we correct for relevant prognostic factors (age, sex, time between trauma and definite treatment, duration of hand therapy) and baseline scores of the Michigan Hand Questionnaire. In an additional step, we will correct for surgeons depending on the number of treating surgeons as well as the number of patients per treating surgeon. Results will be presented as differences between treatment and control with 95% Confidence intervals. The intervention will be labeled as non-inferior when the noninferiority margin of 8 lies outside the 95% CI of this difference, regarding the Michigan Hand Questionnaire measured at 6 months as our primary endpoint. In case missing data did not happen randomly, but was related to specific factors (e.g. more missing data for men than for women), we will correct for this. In an additional analysis, the absolute MHQ scores at 6 months will be adjusted for differences in baseline MHQ scores between the intervention and control group. The secondary outcomes: PSFS, EQ5D, ROM, Kapandji score, grip strength, pinch strength and pain will be analyzed in a similar manner. Differences between the two treatment groups in complication rates will be analyzed using the Chi-square test or the Fischer's Exact test (in case the expected incidence was less than five).

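### The model that decides non-inferiority adjusts for two variables completed after randomisation, so its coefficient need not be the intention-to-treat difference to which the margin of 8 applies

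*Protocol*

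**What the plan says.** Protocol section 7 states the principle "Data will be analyzed following intention-to-treat". It then describes a mixed model "in which we correct for relevant prognostic factors", listed as "age, sex, time between trauma and definite treatment, duration of hand therapy", together with baseline MHQ. The verdict is tied to that model: "The intervention will be labeled as non-inferior when the noninferiority margin of 8 lies outside the 95% CI of this difference". The secondary outcomes are to be analysed in a similar way. A further analysis adjusts 6-month MHQ for baseline MHQ, but the margin is not attached to it.

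Section 5.1 gives the timing. At the first outpatient visit, once the diagnosis is confirmed, "the patient meets the inclusion criteria and has provided informed consent, the patient is randomized". In the control arm, "Surgery is scheduled within 5 working days after the outpatient clinic visit". In the cast arm, a patient without a convincing firm endpoint at the 2-week re-examination is scheduled for surgery within 5 working days of that check; the Summary expects this in about 1 in 10. Hand therapy follows 4 weeks of immobilisation in both arms, and "The frequency and duration of hand therapy will be determined by the hand therapist".

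**The concern.** A covariate fixed before allocation can be adjusted for without changing what the treatment coefficient means. A covariate that allocation, or the healing that follows it, can alter does change the meaning. The coefficient then compares patients who happen to share the same therapy duration or delay, and randomisation no longer guarantees that they are alike.

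Both variables fall in this class. Therapy duration accrues entirely after randomisation. Time to definite treatment ends after randomisation for every operated patient, and in the cast arm a late operation is itself a sign of failed healing. That delay belongs to the strategy under test: section 7 plans a separate exploratory look at whether late surgery in the cast arm does worse.

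The single confidence interval that decides the trial is at stake. If the coefficient drifts towards zero when the cast is truly worse by the margin, false non-inferiority becomes more likely than 2.5%. If it drifts the other way, a non-inferior treatment may be missed.

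**Working it through.** **The plan's own figure.** Section 4.4 gives SD 15, margin 8, one-sided alpha 0.025 and power 80%. The normal formula gives n = 2 × 15² × (1.960 + 0.842)² / 8² = 55.2, so 56 per arm. With the noncentral t, power is 79.9% at 56 and 80.6% at 57, which reproduces 57 per arm, or 114 in total. Then 114 × 1.10 = 125.4, rounded up to 126. No covariate enters this calculation.

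**Mechanism A: therapy duration driven by outcome, with no separate effect of arm.** The within-arm correlation ρ is an assumption; the protocol gives none. With true difference δ and SD σ = 15:

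- adjusted difference = δ(1 − ρ²)
- unadjusted SE = 15 × √(2/57) = 2.81
- adjusted SE = 2.81 × √(1 − ρ²) × √(1 + ρ²δ²/(4σ²))
- false non-inferiority rate = 1 − Φ(1.96 − (adjusted difference + 8)/adjusted SE)

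| ρ | adjusted difference at δ = −8 | adjusted SE | false non-inferiority |
|---|---|---|---|
| 0 | −8.00 | 2.81 | 2.5% |
| 0.1 | −7.92 | 2.80 | 2.7% |
| 0.2 | −7.68 | 2.76 | 3.3% |
| 0.3 | −7.28 | 2.69 | 4.5% |
| 0.4 | −6.72 | 2.59 | 7.1% |
| 0.5 | −6.00 | 2.46 | 12.6% |

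A simulation of 20,000 trials per setting gave 4.3%, 7.3% and 12.3% for ρ = 0.3, 0.4 and 0.5. At δ = 0 the formula gives an adjusted difference of 0, so there is no bias.

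**Mechanism B: therapy improves MHQ and its duration differs by arm.** Assume a 3-week gap between arms, an SD of 3 weeks and a benefit of b points per week. The adjusted difference is the total difference minus b × gap (cast minus control).

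- Cast patients have less therapy, total difference −8: b = 0.5 gives −8 + 1.5 = −6.5 and b = 1 gives −8 + 3 = −5. Simulated false non-inferiority is 5.8% and 14.4%.
- Cast patients have more therapy, total difference 0: the adjusted difference is −1.5 or −3, and power falls from about 80% to 50% or 33%.

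**Mechanism C: duration responds to poor healing and also differs by arm by 3 weeks.** The simulated shift is about 2.3 to 3.8 points. False non-inferiority is 10% to 21% if cast patients have longer therapy and below 1% if they have shorter therapy.

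**Time to definite treatment.** Assume surgery on day 3–12, cast on day 3–5, failed casts dated from surgery on day 14–21, and 10% failures scoring 15 points lower.

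- A true −8 becomes about −9.6 (about −9.4 with whole days drawn uniformly).
- With a uniform 0–13 day delay from injury to the ED it becomes about −8.6. Section 4.3 excludes only injuries older than 13 days at the ED.
- If cast treatment is dated from the clinic visit, it stays at −8.0.

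Even if time has no effect on MHQ, its correlation with arm raises the SE. Under assumed day ranges it goes from 2.8 to 3.0 (cast dated from the clinic visit) or 3.5 (dated from the ED), and power falls from about 81% to 76% or 64%. A wider spread of injury-to-ED delay would weaken that correlation and reduce the cost.

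**The case against.** The strongest reply is that the size and direction are not established, and that stands. The protocol gives no relation of either variable to MHQ. It does not say that therapists lengthen therapy when recovery is slow, and section 5.1 adds that therapists from all hospitals will agree a treatment protocol, with the same week-4 step in both arms. If duration is unrelated to arm and outcome, and time has no effect on MHQ, there is no bias. The calculations also use one time point and omit baseline MHQ, age and sex, whereas the plan is a longitudinal model, so the percentages are illustrations.

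Three stronger readings are tempting, and the protocol does not support them.

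- A reader might infer that the adjustment favours a false claim of non-inferiority. It can, but mechanisms B and C run either way, and the time covariate in the example moves the estimate against the cast.
- A reader might infer that time to treatment is essentially a marker of arm. Part of it, the interval from injury to the clinic, precedes randomisation and is a legitimate baseline quantity.
- A reader might infer that the damage could not be undone. The model can be refitted without the two variables, and the planned additional baseline-adjusted analysis names neither.

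That additional analysis does not answer the point, because the margin rule belongs to the main model. Nor can the matter be left to an analysis plan, since the protocol itself names the covariates.

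**Conclusion.** The point holds in this form: two covariates in the deciding model are completed after randomisation and can depend on the allocated strategy or on healing. The coefficient therefore need not be the intention-to-treat difference for which the margin was set. Definite treatment is also undefined for the cast arm (emergency department cast, clinic cast or later surgery), so that covariate has no common meaning across arms.

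That the bias can occur follows from the text; its size does not. Under the assumed correlations of 0.3 to 0.5 and a true difference at the margin, false non-inferiority is about 4.5% to 12%. At correlations of 0.1 to 0.2 it is about 3%, and the sign can reverse under other mechanisms. Duration of hand therapy is the stronger half of the point. For time to treatment, the shift depends heavily on how the cast arm is dated, and loss of precision is the other cost. Because the primary conclusion rests on this one coefficient, the covariate list should be changed before the data are analysed.

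**What to change.** In section 7, base the primary non-inferiority contrast only on pre-randomisation covariates: baseline MHQ, age, sex and, if delay is thought prognostic, days from trauma to randomisation. Apply the same list to the secondary models. Report duration of hand therapy and time to definite treatment by arm, or use them only in an analysis labelled exploratory. If the latter variable is kept there, define its end date for cast patients.

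The cost is a short change to the covariate sentence, by amendment or in the analysis plan. It needs no new data and puts no burden on patients, and the sample size stays at 114 evaluable and 126 included.

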Rationale: Guidelines recommend surgery for complete Ulnar Collateral Ligament (UCL) ruptures, including Stener lesions. This recommendation is based on expert opinion, anatomic theories and low quality observational case series. High quality studies comparing cast immobilization with operative treatment are lacking. We hypothesize that cast immobilization is non-inferior regarding functional outcome and carries concomitant lower costs compared with operative treatment for complete UCL ruptures, including Stener Lesions.

Objective: To compare functional outcomes and cost-effectiveness of cast immobilization with immediate surgical treatment.

Study design: Multicenter randomized controlled trial (RCT) with 12 months follow-up. **Study population:** Adult patients of 18 years and above, requiring treatment for an acute complete UCL rupture, including Stener Lesions.

Intervention: Non-operative treatment with a cast to immobilize the thumb. After 2 weeks the thumb will be re-examined to determine if surgery is required. It is expected that at re-evaluation at 2 weeks after starting the cast treatment about 1 in 10 patients will still need surgery. The intervention is compared to surgery, which is standard treatment.

Main study parameters/endpoints: Hand function expressed as the Michigan hand outcome questionnaire (MHQ) score at 6 months (from date of injury to 6 months after).

Nature and extent of the burden and risks associated with participation, benefit and group relatedness: It is expected that about 1 in 10 patients who started with cast immobilization will need surgery during re-evaluation at 2 weeks after starting the cast immobilization, meaning completing the treatment will take 2 weeks more for these patients. Patients need to fill in questionnaires, which takes about 2 hours (maximum) over a period of

V7 01-02-2024 8 of 30

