4.4 Sample size calculation

This sample size calculation is based on our primary endpoint (hand function at 6 months expressed as MHQ score 6 months after injury) and calculated using G Power 3.1.9.2. The MHQ score of an individual without any complaints of the hand is 100. The lowest score, indicating worst pain and severe impairment, is zero. The hypothesis will be assessed using a non-inferiority design. The results from two earlier studies on the subject were used for sample size calculation. [4,5] We used a one-sided significance level of 0.025 and a power of 80% with a standard deviation (SD) of 15, and setting our non-

V7 01-02-2024 12 of 30

inferiority limit at 8. The non-inferiority limit of 8 is based on the previous estimated minimal clinically important difference (MCID) of 15 points, divided by 2 and rounded up to 8. A total of 114 patients will be needed to demonstrate non-inferiority of our hypothesis. Each treatment arm will need 57 patients. Including consideration for a potential 10% loss to follow-up, the total number of patients to be included, set at 114, is multiplied by a factor of 1.10. This results in a total of 126 patients to be included.". The MCID of 15 is based on the average of the MCID's of 23, 13 and 8 for the pain, function and work domains, respectively in patients with carpal tunnel syndrome (CTS). [4] The MCID in MHQ score for patients with thumb injury is not yet investigated. Therefore, we decided to use the MCID of CTS patients.

Considering the uncertain outcome of the control group treatment in terms of MHQ-scores for patients with UCL-ruptures, an independent statistician will assess if the sample size calculation needs adjustment, based on the mean change in MHQ-score and SD in the control group, after half of the patients past their 6-month follow-up (N=28).

V7 01-02-2024 13 of 30

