5.2 Summary of findings from clinical studies

Two systematic reviews are available on the treatment of complete UCL ruptures. [8,9] Both studies investigated nonoperative and operative treatment of patients with an acute complete tear of the UCL and concluded that no studies directly comparing nonoperative treatment with operative treatment were present. Regarding the current evidence, nonoperative treatment of complete UCL ruptures, including Stener Lesions, has been shown to be effective in most patients. [2,3] Although the ligament sometimes heals with slight laxity, there is no evidence for any benefits to surgery that outweigh the risks of nonoperative treatment.

Pichora et al observed 32 patients with a complete tear, with and without Stener Lesions, treated with bracing for 1 year. [2] Final laxity measured 2.3° on average; 91% of patients either felt normal or had minimal disability. Functional outcomes such as motion, timed dexterity, and grip and pinch strength measured 89% to 99% of the uninjured side. Three patients required secondary surgery. Landsman et al reported 6 out of 40 patients treated nonoperatively (15%) requested surgery, although they included several bony avulsions. [3]

The proposed intervention for complete UCL ruptures, including Stener Lesions, is a trial of cast immobilization with repeat examination after 2 weeks. There is no evidence that suggests that such a delay negatively affects the outcome if surgery is needed. Thumb immobilization of a complete tear is well described and frequently a successful method of treatment. However, qualitative, focused studies comparing cast immobilization with operative treatment are lacking.

V7 01-02-2024 17 of 30

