In theory, surgery in the intervention arm could result in an unexpectedly suboptimal outcome compared to immediate surgery. To determine whether this is the case, an exploratory analysis will be performed by ranking the changes in MHQ in the entire group of patients who (eventually) underwent surgery and comparing the mean rankings. If the mean ranking of the subgroup that eventually underwent surgery in the intervention arm indicates a suboptimal outcome (mean ranking more than 2 different in the direction of worsening to the detriment of the intervention arm), a critical event committee will be established to assess, based on a relevant extract from the patient file, whether direct surgery would have resulted in a different outcome. To increase the uncertainty for the committee and to avoid assessment bias, several directly operated patients from the control group will also be added to the set to be assessed. The qualitative reporting of the CEC assessment will be of a descriptive nature.

V7 01-02-2024 24 of 30

COST EFFECTIVENESS ANALYSIS

This evaluation focuses on the question if the proposed intervention for patients with a complete UCL rupture, including Stener Lesions, using initial nonoperative treatment, is cost-effective compared to operative treatment. The economic evaluation will be performed as a cost-effectiveness (CEA) as well as a cost-utility analysis (CUA) from the societal as well as health care perspectives. [13] The primary economic outcome for the CEA is the costs per unit change in overall hand function and closely relates to the clinical outcome measure. The CEA is performed to enable identification of diagnostic or interventional strategies to be preferred economically in the field of hand surgery. The primary economic outcome for the CUA is the costs per quality adjusted life year (QALY). The CUA is performed to enable priority setting during health care policy making across disease areas and health care settings.

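### The 2-rank trigger for judging delayed surgery lies well inside chance variation and is crossed about 40% of the time when there is no difference

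*Protocol*

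**What the plan says.** Protocol section 7 (Statistical analysis) raises the possibility that surgery after a failed cast gives a worse result than immediate surgery. It plans an exploratory analysis of this by "ranking the changes in MHQ in the entire group of patients who (eventually) underwent surgery and comparing the mean rankings". The decision rule is a "mean ranking more than 2 different in the direction of worsening to the detriment of the intervention arm". The text treats a gap of that size as showing a suboptimal result in the converted subgroup. If it occurs, "a critical event committee will be established to assess, based on a relevant extract from the patient file" whether immediate surgery would have led to a different result. Files of some directly operated controls are mixed in to limit assessment bias. On output: "The qualitative reporting of the CEC assessment will be of a descriptive nature". No basis, interval or error rate is given for the value 2.

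The group sizes come from elsewhere in the protocol. The Summary expects that "about 1 in 10 patients will still need surgery" at the two-week re-evaluation. Section 4.4 states "Each treatment arm will need 57 patients" and, after allowance for loss to follow-up, "This results in a total of 126 patients to be included". Section 5.2 gives a higher conversion figure from an earlier series: "6 out of 40 patients treated nonoperatively (15%) requested surgery".

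**The concern.** The number 2 is fixed in the protocol as the dividing line between an acceptable and a poorer result. A mean rank based on about six patients among some sixty moves a great deal by chance, so a gap of 2 carries almost no information about delay.

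Two things follow. When delay makes no difference, the report may still carry the protocol's own label of a suboptimal result. When delay does harm, the rule can stay silent, and then no file is looked at.

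The comparison also sets a selected group, cast patients without a clearly firm endpoint at re-examination (section 5.1), against all operated controls. A lower mean rank could therefore reflect the injury rather than the delay.

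**Working it through.** **Inputs**
- Evaluable patients per arm: 57 (section 4.4).
- Conversion: about 1 in 10 (Summary), so 0.10 × 57 = 5.7, about 6. At 15% (section 5.2), 0.15 × 57 = 8.6, about 9.
- SD 15 and margin 8 MHQ points (section 4.4).
- Threshold: 2 ranks, one direction (section 7).

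**The plan's own figure.** The protocol gives no operating characteristic for the trigger. The only figure to reproduce is the sample size that supplies the group sizes. With margin 8, SD 15, one-sided 0.025 and true difference 0, noncentral-t power is 0.799 at 56 per arm and 0.806 at 57. So 57 per arm (114 in total) reproduces, and 114 × 1.10 = 125.4, rounded up to 126.

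**Chance variation of the statistic.** With n1 converted and n2 directly operated patients, N = n1 + n2, exchangeable groups and no ties:

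SD = √[ N(N+1)/12 × (1/n1 + 1/n2) ]

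For n1 = 6, n2 = 57, N = 63: 63 × 64/12 = 336; 1/6 + 1/57 = 0.1842; 336 × 0.1842 = 61.9; SD = 7.87 ranks. The threshold is 2/7.87 = 0.25 SD.

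**Chance of a trigger with no difference.** The normal approximation gives P(Z > 0.254) = 0.400. The exact permutation distribution gives 0.405 and simulation 0.41.

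| Converted vs directly operated | SD of difference (ranks) | P(trigger), no difference (exact) |
|---|---|---|
| 4 vs 57 | 9.18 | 0.417 |
| 6 vs 57 | 7.87 | 0.405 |
| 6 vs 63 | 8.57 | 0.414 |
| 9 vs 57 | 6.89 | 0.384 |
| 12 vs 57 | 6.37 | 0.380 |

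If the rule is read as distance from the overall mean rank rather than from the control mean rank, 6 versus 57 gives 0.388.

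**How little moves the statistic.** If one of the six converted patients shifts by k places, the mean-rank difference changes by k × (1/6 + 1/57) = 0.184k. A shift of about 11 places in 63 by a single patient (2/0.184 = 10.9) changes it by 2.

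**Behaviour under a true deficit.** This step assumes normally distributed changes with SD 15. The protocol gives 15 for the sample size calculation on the 6-month score and states no SD for change. For 6 versus 57, by simulation:

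| True deficit (MHQ points) | Trigger | No review opened |
|---|---|---|
| 0 | 0.41 | 0.59 |
| 4 | 0.65 | 0.35 |
| 8 | 0.84 | 0.16 |
| 15 | 0.98 | 0.02 |

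**Would a stricter threshold help?** On the same assumption, the SE of the mean difference is 15 × √0.1842 = 6.44 points. A trigger at 8 points has a false-trigger rate of P(Z > 8/6.44) = 0.107, but detects a true 8-point deficit only 50% of the time. A trigger at 10 ranks has a false-trigger rate of about 10% and detects an 8-point deficit about 47% of the time. With about six converted patients, no cut-off gives both few false alarms and few misses.

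**The case against.** The strongest defence is that this is a screen and not a test. The analysis is labelled exploratory, crossing the line only opens a file review, and the report of that review is descriptive. A false alarm costs the reading of about six files and some controls, so a low threshold favours sensitivity. The committee, not the rank gap, is asked the causal question, and control files are mixed in for that purpose. All of this stands, and it limits the consequence.

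It does not rescue the rule as written. The protocol does not present 2 ranks as a sensitive screen; it reads the gap as a sign of a suboptimal result. If a review is cheap enough to hold on chance alone four times in ten, it is cheap enough to hold always, which removes the missed reviews too.

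Three stronger readings are tempting but unsupported:
- A reader might infer that the rule is no better than a coin toss. That roughly describes the case of no difference, but under the SD assumption the rule responds 84% of the time at an 8-point deficit. It is sensitive and unspecific, not uninformative.
- A reader might infer that this is the trial's chief safety safeguard. The protocol does not say so: section 7 calls the possibility theoretical, section 5.2 reports no evidence that such a delay worsens the outcome, and section 6.7 assumes that both strategies are sufficiently safe.
- A reader might infer that the main conclusion is at risk. The rule does not enter the primary non-inferiority comparison, the sample size review or any stopping decision.

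**Conclusion.** The point holds as a defect in a fixed rule, of low to moderate severity. A gap of 2 mean ranks cannot show that delayed surgery gave a poorer result: it is a quarter of one chance SD and is exceeded about 40% of the time with no difference. That figure needs no assumption about the spread of MHQ. It rests on exchangeable groups without ties and on roughly 6 versus 57 operated patients, and it stays at 38% to 42% for 4 to 12 converted patients. The rates of missed review (about 35% at 4 points, 16% at 8) depend further on the assumed SD of 15 for change.

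Separately, the contrast is not randomised. Even a large gap could come from selection of the cast failures, and that selection could also move the trigger rate away from 40% without any harm from delay.

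**What to change.** In section 7:
1. Remove the 2-rank trigger and the statement that such a gap shows a suboptimal result.
2. Send every cast-arm patient who is eventually operated on (about six expected), together with the control files already planned, to the committee regardless of ranks.
3. Report the difference in MHQ change between converted and directly operated patients with its 95% CI, labelled exploratory and non-randomised. At an SD of 15 the half-width would be about 1.96 × 6.44 = 12.6 points, which shows the reader how little six patients can settle.
4. Do not substitute an 8-point or 10-rank trigger. Either would detect a true 8-point deficit only about half the time.

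The cost is a change of protocol wording. The one downside is that the committee always convenes, for about six converted files plus controls.
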